16.2.2. Laboratory Reference Ranges and Potentially Clinically Significant (PCS)

Quantitative laboratory measurements will be compared with the relevant laboratory reference ranges in SI units and categorized as:

Low: Below the lower limit of the laboratory reference range.

Normal: Within the laboratory reference range (upper and lower limit included).

High: Above the upper limit of the laboratory reference range.

Similarly, sponsor defined- PCS laboratory results will be identified using the criteria in Appendix 3.

16.3. ECG Evaluations

The number and percentage of subjects with ECG results will be presented as Normal, Abnormal and Not Evaluable. A subject will be counted in the worst result for the post-baseline value.

ECG results will be presented in a data listing.

16.4. Vital Signs

Vital signs (supine systolic and diastolic blood pressures, respiratory rate, pulse rate, and oral temperature) and weight will be summarized using descriptive statistics at baseline and each evaluation visit. Change from baseline will be included in this presentation as well. In addition, the number and percentage of subjects with vital sign PCS criteria in Table 4 will be presented.

Data listings of vital signs and PCS criteria will be provided.

Table 4. Vital Signs Potentially Clinically Significant (PCS) Criteria

Variable	Unit	Low	High
Supine SBP	mmHg	< 90 mmHg AND change from baseline ≤ -20 mmHg	> 180 mmHg AND change from baseline ≥ 20 mmHg
Supine DBP	mmHg	< 50 mmHg AND change from ≤ -15 mmHg	> 105 mmHg AND change from baseline ≥ -15 mmHg
Supine Pulse rate	beats/min	< 50 bpm AND change from baseline ≤ -15 bpm	> 120 bpm AND change from baseline ≥ 25 bpm

Variable	Unit	Low	High
Weight	Kg	percentage change from baseline \leq -7.0 %	percentage change from baseline \geq 7.0 %

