11.3.4. Vital Signs

Supine systolic and diastolic blood pressures, respiratory rate, pulse rate, and oral temperature will be measured following 5 minutes of seated rest.

Blood pressure and pulse rate should first be taken with the subject in the supine position after resting for \geq 5 minutes. Blood pressure and pulse rate will be taken again after standing for 2 to 4 minutes. The same arm should be used during each assessment of blood pressure and pulse rate throughout the study. If a subject develops symptoms consistent with orthostatic hypotension

(light-headedness, dizziness, or changes in sensorium upon standing) at any point, his or her supine and standing blood pressure and pulse rate should be collected at that time in the manner described above. Vital signs will be obtained prior to clinical laboratory collection and performance of an ECG.

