15.3.8.6. Vital Signs and Weight

Vital signs (supine systolic and diastolic blood pressures, respiratory rate, pulse rate, and oral temperature) and weight will be summarized using descriptive statistics at baseline and each evaluation visit. Change from baseline will be included in this presentation as well. In addition, a subject incidence (and percentage) of potentially clinically significant vital signs values will be presented.

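### Standing blood pressure and pulse are collected but have no planned summary or PCS criterion, so postural falls get no measurement-based count; separately, the rest instruction for supine readings needs reconciling

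*SAP*

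**What the plan says.** **Collection.** Protocol 11.3.4 gives the supine measurement first and then says: "Blood pressure and pulse rate will be taken again after standing for 2 to 4 minutes". If a subject develops symptoms suggesting orthostatic hypotension, "his or her supine and standing blood pressure and pulse rate should be collected at that time in the manner described above". Protocol Table 2 and SAP 3.5 mark vital signs at Visits 1 to 9 and at the EDV.

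**Analysis.** Protocol 15.3.8.6 defines the analysed set as "Vital signs (supine systolic and diastolic blood pressures, respiratory rate, pulse rate, and oral temperature) and weight". SAP 16.4 repeats it: "Vital signs (supine systolic and diastolic blood pressures, respiratory rate, pulse rate, and oral temperature) and weight will be summarized using descriptive statistics". SAP Table 4 has PCS rows for supine systolic pressure, supine diastolic pressure, supine pulse and weight. The low systolic rule, for example, is "< 90 mmHg AND change from baseline ≤ -20 mmHg".

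**Stated departures.** SAP 3.4.2 reports one change from the protocol's analyses, concerning drug accountability. It says nothing about standing vital signs.

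**Rest before the supine reading.** The opening sentence of protocol 11.3.4 is "Supine systolic and diastolic blood pressures, respiratory rate, pulse rate, and oral temperature will be measured following 5 minutes of seated rest". The next paragraph begins "Blood pressure and pulse rate should first be taken with the subject in the supine position after resting for" at least 5 minutes.

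**The concern.** A standing reading a few minutes after a supine one serves mainly to show the postural change, and the symptom-triggered repeat confirms that this is part of its purpose here. Yet neither document defines a standing summary, a supine-to-standing difference or an orthostatic criterion. The vital-signs tables could look unremarkable while the reading that bears on postural change goes unsummarised.

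The study also tabulates dizziness and unsteadiness as LAEP items. Without the postural readings, those symptom scores cannot be set against the pressures measured at the same visits.

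The rest wording is a second, independent matter. It concerns the only blood pressure value that is analysed: if sites read the two sentences differently, change from baseline could mix readings taken after different rest postures.

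**Working it through.** No figure in the plan needs reproducing. The check compares what is collected with what is analysed, tests the Table 4 logic and sizes the data affected.

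**1. Collected against analysed**

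| Quantity | Collected (protocol 11.3.4) | By-visit summary (SAP 16.4) | PCS rule (SAP Table 4) |
|---|---|---|---|
| Supine systolic and diastolic pressure | Yes | Yes | Yes |
| Supine pulse | Yes | Yes (the text says only pulse rate) | Yes |
| Standing systolic and diastolic pressure | Yes | None | None |
| Standing pulse | Yes | None | None |
| Same-visit supine-to-standing change | Derivable | None | None |

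**2. Table 4 logic.** Each pressure or pulse flag needs an extreme supine value and a change from baseline. The same-visit difference enters no rule. Illustration with assumed values: supine systolic 125 mmHg at baseline and at a visit, standing 95 mmHg at that visit.
- Postural change: 95 − 125 = −30 mmHg.
- Low systolic rule: 125 is not below 90, and the supine change is 125 − 125 = 0, which is not ≤ −20. No flag.
- Even if the standing value were put through the supine rule, 95 is not below 90, so there is still no flag.

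**3. Symptom-triggered pairs.** SAP 6.4 keeps unscheduled post-baseline readings out of by-visit summaries but lets them contribute to vital-signs PCS values. For a pair taken outside a scheduled visit, the supine half can count; the standing half has no rule to meet.

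**4. How much data.** Inputs: about 100 subjects, 50 per arm (SAP 3.1), and completion of 60% and 50% (SAP 3.3).
- Ceiling over all scheduled visits: 9 × 100 = 900 pairs. This includes Visits 1 and 2, which precede or coincide with first dispensing.
- On-treatment visits are Visits 3 to 9, that is 7 visits; ceiling 7 × 100 = 700.
- Completers: 0.60 × 50 + 0.50 × 50 = 55. Full attendance gives 55 × 7 = 385 pairs.
- The other 45 subjects contribute between 0 and 6 scheduled visits each (Visits 3 to 8), so 0 to 270 pairs, plus up to 45 EDV pairs.
- Range: 385 to 385 + 270 + 45 = 700.

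The protocol's own target of about 190 subjects would make these counts roughly 1.9 times larger.

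**5. What an incidence could show.** With 50 subjects in an arm and no events, the exact two-sided 95% upper limit is 1 − 0.025^(1/50) = 7.1%. The count would be informative but coarse.

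**6. Rest wording.** Both sentences have pressure read supine. The first specifies a seated rest; the second gives a minimum rest time without clearly stating the posture during it. They can be read as one procedure or as two.

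**The case against.** A reader might infer that orthostatic falls cannot appear in any output. The documents do not support that:
- Protocol 12.2 has clinically significant objective findings recorded as adverse events, and SAP 16.1.1 tabulates these by arm, system organ class and preferred term.
- SAP 16.6.2 summarises each LAEP symptom, including dizziness and unsteadiness.
- The vital-signs listing in SAP 16.4 is not limited to supine values.

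These routes exist but do not replace the analysis. Adverse event capture depends on investigator judgement, with no postural criterion given, and on the non-leading questioning of protocol 11.3.1. LAEP items record symptoms, not pressures. A listing gives no incidence.

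It can also be said that protocol and SAP agree on the supine-only list, that no orthostatic analysis is promised, and that the vital-signs endpoint is served by the supine summary. All of that is correct: this is not a departure of the SAP from the protocol. The study is also uncontrolled, with no testing and no comparison of arms, so an orthostatic count would be descriptive and could not be attributed to the drug. The same holds for every PCS row already planned, so this limits interpretation without justifying the omission.

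Two further inferences fail. The seated/supine wording does not cause the postural gap; it affects only the consistency of supine readings. Nor is it shown that a site cannot follow both sentences, because a subject could rest seated and then be measured supine. It is an ambiguity, and the documents give no basis for estimating any added variability.

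**Conclusion.** The point holds in a limited form. Standing blood pressure and pulse are required at up to nine site visits and the EDV, and no planned vital-signs summary or PCS criterion uses them. What is lost is a systematic, measurement-based description of postural change, above all for asymptomatic falls. Falls judged clinically significant can still reach the adverse event tables.

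On the SAP's assumptions, 385 to 700 on-treatment pairs are affected. The primary endpoint and the seizure endpoints are not touched. This is a safety-reporting gap worth closing because the data should already exist.

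The conclusion assumes that standing values were entered in the database as protocol 11.3.4 requires, and that the output templates mentioned in SAP section 8, which are not part of the documents reviewed, add no standing summary.

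The rest instruction is a separate and smaller inconsistency. The documents do not show which wording is intended, and no conclusion is drawn on that.

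**What to change.** 1. **SAP 16.4:** add a by-visit descriptive summary, by arm, of standing systolic and diastolic pressure, standing pulse and the same-visit supine-to-standing change. Include the pre-dose pair, so that post-baseline findings can be read against the postural change already present.
2. **SAP Table 4:** add one orthostatic row, with the criterion chosen by the sponsor and fixed before database lock. State that unscheduled symptom-triggered pairs count towards it, in line with SAP 6.4.
3. **SAP 3.4.2:** if standing values were not captured, or are deliberately left unanalysed, say so and give the reason.
4. **Protocol 11.3.4:** reconcile the two descriptions of rest so that one rest position applies at all sites and visits. If visits have already taken place, record how sites carried out the instruction.

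Cost: some SAP text, one table, one PCS row and one clarifying protocol sentence. No new measurements are needed. The drawback is one more descriptive table whose uncontrolled counts, from about 50 subjects per arm, need cautious reading.

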6.7. Common Calculations

For quantitative measurements, change from baseline will be calculated as:

Test Value at Visit X – Baseline Value

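### The High criterion for supine diastolic pressure in SAP Table 4 has the wrong sign on the change, so readings above 105 mmHg are flagged without any rise from baseline

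*SAP*

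**What the plan says.** SAP section 16.4 commits to a count: "the number and percentage of subjects with vital sign PCS criteria in Table 4 will be presented". It also commits to listings. Table 4 pairs an absolute limit with a change from baseline for the two pressures and pulse, and uses percentage change alone for weight:

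- Supine diastolic: High is "> 105 mmHg AND change from baseline ≥ -15 mmHg"; Low is "< 50 mmHg AND change from ≤ -15 mmHg".
- Supine systolic: High is "> 180 mmHg AND change from baseline ≥ 20 mmHg"; Low is "< 90 mmHg AND change from baseline ≤ -20 mmHg".
- Supine pulse: High is "> 120 bpm AND change from baseline ≥ 25 bpm"; Low is below 50 bpm with a change of −15 bpm or lower.
- Weight: High is a gain of 7.0% or more; Low is a loss of 7.0% or more.

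SAP section 6.7 fixes the sign convention for change: "Test Value at Visit X – Baseline Value". SAP section 6.4 lets unscheduled post-baseline measurements contribute to the vital-sign PCS results. Protocol section 15.3.8.6 promises the incidence of PCS vital signs but gives no thresholds, so Table 4 is the only specification, and nothing elsewhere overrides the cell.

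**The concern.** In the other three High cells the change must be a rise. In all four Low cells it must be a fall. The diastolic High cell is the only one whose change condition points the wrong way, and its −15 is the figure in the Low cell beside it. The two conditions are joined by AND, so the second was meant to narrow the first. With a minus sign it narrows almost nothing.

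A PCS criterion that includes change from baseline is there to separate values that became abnormal on treatment from values that were abnormal already. Programmed as written, the diastolic line would mix the two and would count some improvements as High. Eligibility sets no blood pressure limit, and Protocol section 8.2, criterion 16, allows minor or well-controlled conditions, so subjects with raised baseline diastolic pressure can enter. Both arms receive eslicarbazepine and there is no untreated control, so no comparator count would show up the inflation.

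**Working it through.** **Inputs.** The rule as printed and the pattern of the other rows come from SAP Table 4; the definition of change comes from SAP section 6.7. Write B for baseline and V for the post-baseline reading, in whole mmHg.

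**Rule as printed.** Flag if V > 105 and V − B ≥ −15, that is, V > 105 and B ≤ V + 15.

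**Rule with the sign used in the other High cells.** Flag if V > 105 and V − B ≥ +15, that is, V > 105 and B ≤ V − 15.

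**At V = 106**, the lowest whole reading above the limit:

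- Printed: B ≤ 106 + 15 = 121.
- Sign reversed: B ≤ 106 − 15 = 91.
- Baselines on which the two rules disagree: 92 to 121 mmHg.

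**When the printed change condition excludes anyone.** It needs B > V + 15 with V ≥ 106, so B ≥ 122 mmHg. For any subject with a lower baseline the criterion is simply a reading above 105 mmHg.

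**Examples.**

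| Baseline → reading | Change | Printed rule | Rise of ≥ 15 |
|---|---|---|---|
| 121 → 106 | −15 | flagged | not flagged |
| 110 → 106 | −4 | flagged | not flagged |
| 106 → 106 | 0 | flagged | not flagged |
| 104 → 107 | +3 | flagged | not flagged |
| 100 → 106 | +6 | flagged | not flagged |
| 91 → 106 | +15 | flagged | flagged |
| 95 → 110 | +15 | flagged | flagged |
| 122 → 106 | −16 | not flagged | not flagged |

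**Illustration under assumptions.** The documents give no diastolic distribution. Baseline and post-baseline readings were therefore simulated as bivariate normal and rounded to whole mmHg, with no mean change. The mean was set at 75, 80 or 85 mmHg, the SD at 9 or 11 mmHg, and the correlation at 0.5 or 0.7. Across the twelve combinations:

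- 0.04% to 3.1% of readings exceeded 105 mmHg.
- The printed rule flagged at least 99.8% of those readings. With mean 80, SD 11 and correlation 0.5, for example, it flagged 1.0265% of all readings, against 1.0277% above 105 mmHg.
- Of the readings flagged as printed, 40% to 87% did not rise by 15 mmHg, and 3% to 19% did not rise at all.

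These are shares of readings, not of subjects, and they are not predictions for this trial.

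**Weight of one subject.** With about 50 per arm (SAP section 3.1), one misclassified subject moves an arm's percentage by 1/50 = 2 points. With the 93 and 97 in Protocol section 15.1 the shift is 1/93 = 1.1 or 1/97 = 1.0 points.

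**The case against.** The column is headed High, not increase, and every flagged reading must still exceed 105 mmHg. Nobody with an ordinary diastolic pressure is flagged, and no high reading is invented. That is true, and it limits the harm. It does not explain why the cell contains a change condition that hardly acts, when the other High cells contain one that does.

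The error runs in one direction. Any reading that meets a +15 rule also meets the printed rule, so no genuine case is lost. This stands: the fault is over-counting, not a missed signal.

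A baseline of 92 mmHg or more is necessary for misclassification but not sufficient. The subject also needs a post-baseline reading above 105 mmHg, with a change from −15 to just under +15. A subject who stays at 95 is unaffected, and one who goes from 95 to 110 is flagged under either rule. The count therefore depends on baseline and post-baseline values jointly. This stands too.

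The value +15 is not written anywhere. High and Low mirror each other for systolic pressure and weight but not for pulse, where Low uses −15 and High uses +25. So the wrong sign is plain from the table, while the size of the intended rise is an inference, though the natural one.

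Finally, the analysis is descriptive, with no testing or comparison between arms (SAP sections 6.1 and 6.6), and the vital-sign listings would let a careful reader trace a flagged subject. That reduces the consequence, but the summary table would still be wrong.

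**Conclusion.** The criterion is wrong as written. The sign on the diastolic High change condition contradicts the rest of Table 4, and the condition excludes only subjects whose baseline was at least 122 mmHg. Following the SAP exactly would report level or slightly improved readings above 105 mmHg as High PCS values. At 106 mmHg the disputed baselines run from 92 to 121 mmHg. The damage is confined to one line of a descriptive safety table, any tabulation or listing built from the same flag, and no efficacy or primary result. The number of subjects affected is unknown and may be small. The conclusion about the sign needs no distributional assumption, only the definition of change in SAP section 6.7 and the pattern of the other cells. The reading of +15 as the intended threshold is an inference for the sponsor to confirm.

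**What to change.** In SAP Table 4, change the supine diastolic High criterion to above 105 mmHg with a change from baseline of at least 15 mmHg, once the sponsor has confirmed that 15 is the value intended. Make the same change in the program specification, so that the PCS count and the listing use one definition. In the same edit, supply the word baseline that is missing after the change wording in the diastolic Low cell. The cost is one character and one word in the SAP plus a check of the derivation code. No data collection, other analysis or study procedure changes.

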16.5. Physical/Neurological Examination

All physical and neurological exam findings at screening will be captured in the medical history and summarized together with the other medical history events. Clinically significant changes from the screening visit will be captured as AEs as appropriate and summarized together with the other AEs. A listing displaying whether a physical examination was performed for each subject and the date of the physical examination will be provided.

16.6. Other Safety Assessments

16.6.1. Electronic Columbia Suicide Severity Rating Scale (eC-SSRS)

The eC-SSRS is a tool designed to systematically assess and track suicidal behavior and suicidal ideation for life time prior to the screening visit, and throughout the study. The strength of this suicide classification system is in its ability to comprehensively identify suicidal events while limiting the over-identification of suicidal behavior. The eC-SSRS Baseline/Screening Version is used at the screening visit and the eC-SSRS Since Last Visit Version is used from Visit 2 onward.

Subjects with complete and incomplete eC-SSRS records in the same visit, both records will be included in the listing.

Subjects who have complete and incomplete eC-SSRS records in the same visit, only complete records will be included in the summary tables. otherwise the incomplete record will be included in the tables.

eC-SSRS includes four sections: Suicidal Ideation, Intensity of Ideation, Suicidal Behavior, and Answer for Actual Suicide Attempts.

The following outcomes are eC-SSRS categories and have binary responses (yes/no). The categories are re-ordered from the scale to facilitate the definitions of the eC-SSRS endpoints, and to provide clarity in the presentation of the results.

Suicidal ideation is measured by 5 categories, representing 5 subtypes of suicidal ideation with increasing severity:

1. Category 1: Wish to be Dead
2. Category 2: Non-specific Active Suicidal Thoughts
3. Category 3: Active Suicidal Ideation with Any Methods (Not Plan) without Intent to Act
4. Category 4: Active Suicidal Ideation with Some Intent to Act, without Specific Plan
5. Category 5: Active Suicidal Ideation with Specific Plan and Intent

Suicidal behavior is measured by 5 categories, representing 5 subtypes of suicidal behavior:

1. Category 6: Preparatory Acts or Behavior
2. Category 7: Aborted Attempt
3. Category 8: Interrupted Attempt
4. Category 9: Actual Attempt (non-fatal)
5. Category 10: Completed Suicide

The 10 categories above are not mutually exclusive. Subjects will be counted in each category for which they have an event.

Self-injurious behavior without suicidal intent is a non-suicide-related eC-SSRS outcome, and has a binary response (yes/no).

For eC-SSRS analysis, “baseline” and “post-baseline” are defined as follows.

Time point	Study Visit	eC-SSRS Version	Derivation Rule
Baseline	Screening/Visit 1	Baseline/Screening – life time, past one months and past two years	Most severe outcome
	Titration/Visit 2	Since Last Visit	

Post-baseline	All post-baseline visits up to and including Week 27/Visit 9, including unscheduled visits	Since Last Visit	Most severe outcome
---------------	--	------------------	---------------------

eC-SSRS composite endpoints will be derived for each time point of interest (i.e. baseline, post baseline, and each study visit) as follows:

Any suicidal ideation: A “yes” answer to any one of the 5 suicidal ideation questions on eC-SSRS (Categories 1-5).

Any suicidal behavior: A “yes” answer to any one of the 5 suicidal behavior questions on the eC-SSRS (Categories 6-10).

Any suicidality: A “yes” answer to any one of the 10-suicidal ideation and behavior questions on the eC-SSRS (Categories 1-10).

For each subject, the suicidal ideation score at each time point of interest (i.e. baseline, post baseline, and each study visit) is defined as the maximum suicidal ideation category (1-5) present for the time of interest. If no ideation is present a score of 0 is assigned. A suicidal ideation score of 4 or 5 is considered serious.

The number and percentage of subjects with any suicidality, any suicidal ideation and subtypes of ideation, any suicidal behavior and subtypes of behavior, and any non-suicidal self-injurious behavior will be presented for:

- Baseline (as defined above)
- Post-baseline (as defined above)
- Each scheduled study visit: Screening (lifetime), Titration/Visit 2, Week 3/Visit 3, Week 7/Visit 4, Week 11/Visit 5, Week 15/Visit 6, Week 19/Visit 7, Week 23/Visit 8, Week 27/Visit 9, EDV.

Shift in suicidal ideation score from baseline to the post-baseline time point and to each the following study visit will be presented: Week 3/Visit 3, Week 7/Visit 4, Week 11/Visit 5, Week 15/Visit 6, Week 19/Visit 7, Week 23/Visit 8, Week 27/Visit 9, EDV.

Intensity of ideation for the most severe ideation subtype is measured in terms of frequency, duration, controllability, deterrents, and reasons for ideation. Each is measured with responses ranging from 0 to 5 for frequency and duration, and from 1 to 5 for controllability, deterrents, and reasons for ideation. The ideation intensity total score is the sum of responses to the five items and can range from 2 to 25 for subjects with endorsed suicidal ideation. If one or more of these five items are missing at an assessment, the total score will be set to missing. If a subject did not endorse any suicidal ideation, a score of 0 for the ideation intensity total score will be given.

Actual lethality associated with actual attempts is rated on a 6-point scale from 0 = ‘No physical damage or very minor physical damage’ to 5 = ‘Death’. Potential lethality of actual attempts (if actual lethality = 0) is rated on a 3-point scale from 0 = ‘Behavior not likely to result in injury’ to 2 = ‘Behavior likely to result in death despite available medical care.

The ideation intensity total score and the actual lethality and potential lethality of actual attempts will be presented in data listings.

16.6.2. Score of AED-specific AEs (by the Liverpool Adverse Event Profile [LAEP]).

The LAEP is designed as a patient self-report scale to assess the frequency of AED side effects. It includes 19 items rated on a 4-point Likert scale with 1, never a problem; 2, rarely a problem; 3, sometimes a problem; and 4, always or often a problem. Total scores range from 19 to 76, with high scores indicating more-frequent symptom reporting.

The LAEP is introduced to the participants in the questionnaire with the heading “Here are a few questions about your health generally.” The recommended preamble to the scale followed with the words, “During the last 4 weeks, have you had any of the problems listed.” The problems include unsteadiness, tiredness, restlessness, feelings of anger or aggression to others, nervousness and/or agitation, headache, hair loss, problems with skin (eg, acne, rash), double or

blurred vision, upset stomach, difficulty in concentrating, trouble with mouth or gums, shaky hands, weight gain, dizziness, sleepiness, depression, memory problems, and disturbed sleep.

The following summaries and listings will be provided for LAEP data:

- The individual LAEP scores and changes from baseline for each evaluation time point will be summarized for each symptom descriptively.
- The total score and change from baseline will be also summarized.
- A listing of LAEP will be provided.

Figure of the mean (+/-SD) change from baseline for the total score by time point and arm will be provided.

17. References

1. A Concordance Correlation Coefficient to Evaluate Reproducibility, L. Lin, Biometrics, Vol. 45, No. 1 (Mar., 1989), 255-268
2. Identifying depression in epilepsy in a busy clinical setting is enhanced with systematic screening, D. Friedman et al, Seizure, 18, 2009, 429-433.
3. SAS Institute Inc. 2009. Base SAS® 9.2 Procedures Guide. Cary, NC: SAS Institute Inc.
4. Base SAS® 9.2 Procedures Guide. Copyright © 2009 by SAS Institute Inc., Cary, NC, USA.

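### When a complete and an incomplete eC-SSRS record exist at one visit, a yes given only on the incomplete record is left out of the suicidality tables

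*SAP*

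**What the plan says.** SAP section 16.6.1 gives three rules for incomplete eC-SSRS records.

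- Tables, when both kinds of record exist at the same visit: "only complete records will be included in the summary tables".
- Tables, when there is no complete record: "otherwise the incomplete record will be included in the tables".
- Listings: "both records will be included in the listing".

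The section does not say what makes a record incomplete, gives no reason for the exclusion, makes no exception for a positive answer on the excluded record, and has no rule for combining the two records.

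The same section sets the counting principle for the ten categories: "Subjects will be counted in each category for which they have an event". Any suicidality is a yes in any of Categories 1 to 10. The ideation score is the highest ideation category present, and 4 or 5 is called serious. For absent ideation, "If no ideation is present a score of 0 is assigned". The derivation rule for the pooled baseline (Visits 1 and 2) and for the pooled post-baseline period is "Most severe outcome".

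The eC-SSRS classification is a listed safety endpoint (protocol section 6.4, SAP section 2.4.4). Protocol section 11.3.7.1 defines ideation by a yes at any evaluation, and protocol section 15.3.8.9 mentions no exclusion of records.

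**The concern.** Suppose a subject discloses ideation, breaks off, and then completes the form at the same visit answering no throughout. The tables show only the second form. Had the subject not repeated it, the disclosure would have been tabulated. Whether a stated yes counts thus depends on whether a repeat was done. Data quality alone does not explain this, because the SAP treats a lone incomplete record as usable.

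The rule also runs against the way the SAP handles other safety data. A missing AE severity is classed as severe (section 16.1.2), a missing relationship is taken as related (section 16.1.3), and the ECG summary uses the worst post-baseline result (section 16.3).

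Breaking off may be related to the answer. Protocol section 11.3.7.1 describes a form in which responses bring up follow-up questions, so a yes can lengthen it. That is an inference; the documents do not report it.

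At stake is a possible undercount in the suicidality tables, which would give no sign that a positive answer had been set aside.

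**Working it through.** The plan states no expected eC-SSRS count, so there is no figure of its own to reproduce. The check is of the rule's logic, followed by the size of one lost subject.

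**Inputs.** The record rules, the category count and the score definition come from SAP section 16.6.1. Arm sizes are about 50 and 50 (SAP section 3.1), and about 93 and 97 (protocol section 7.1). The arm sizes serve only as illustrative denominators.

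**Logic.** For one subject, visit and category, let C = 1 if the complete record says yes and I = 1 if the incomplete record says yes, with 0 for no or blank.

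- SAP rule: T = C if a complete record exists, otherwise T = I.
- Using both records: U = max(C, I).

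U − T is never negative. It equals 1 only when a complete record exists with C = 0 and I = 1. So the rule can remove a positive and can never add one. If the complete record repeats the yes (C = 1), nothing changes.

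The pooled post-baseline result takes the maximum over visits. A lost positive therefore changes the pooled category only if that category is not endorsed at another post-baseline visit.

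**Hypothetical pair at one post-baseline visit.** The incomplete record has yes in Categories 1 and 4; the complete record has no in all ten.

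| | SAP rule | Both records |
|---|---|---|
| Any suicidality | no | yes |
| Ideation score | 0 | max(1, 4) = 4, serious by the SAP's definition |

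**Size of one such subject,** if it is the only positive in the arm:

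| Subjects in arm | SAP rule | Both records | Difference |
|---|---|---|---|
| 50 | 0/50 = 0% | 1/50 = 2.0% | 2.0 points |
| 93 | 0/93 = 0% | 1/93 = 1.1% | 1.1 points |
| 97 | 0/97 = 0% | 1/97 = 1.0% | 1.0 point |

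For scale, the exact (Clopper-Pearson) 95% intervals at 50 subjects are 0 to 7.1% for 0/50 and 0.05 to 10.65% for 1/50. They overlap heavily. What changes is whether the table shows any case at all.

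**Shift tables.** Two cases move in opposite directions.

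- A post-baseline score of 4 is lost and baseline is 0: the table shows 0 to 0 instead of 0 to 4, so a worsening is hidden.
- A baseline score of 2 is lost at Visit 1 or 2, and the post-baseline score is 2: the table shows 0 to 2 instead of 2 to 2, so a worsening appears that did not occur.

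**The case against.** The strongest defence is that a finished questionnaire is better evidence than an abandoned one. Section 16.6.1 itself values limiting the over-identification of suicidal behavior. If records are combined, an answer given in error on an abandoned form can never be corrected. Using one record per visit also matches the general retest convention in SAP section 6.4. The rule is prespecified, both records are listed, no statistical tests are planned (section 6.6), and protocol section 11.3.7.1 asks the investigator to evaluate anyone who expresses ideation or behavior, however the answers are tabulated. From Visit 2 onward the form asks about the interval since the last visit, so a completed repeat may well restate a true yes.

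Most of this stands, and it keeps the point small. It does not explain why the same unfinished form is acceptable evidence when it is the only one, and a listing does not change a table.

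A reader might infer that the rule contradicts the most-severe-outcome derivation. The text does not support that. The derivation says how visits are pooled, the record rule says what represents one visit, and the two can be applied in sequence. The inclusion of unscheduled visits does not bear on duplicate records within a visit. The real tension is with the statement that subjects count in every category in which they have an event.

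**Conclusion.** The point holds as a minor reporting weakness. A yes found only on an incomplete record is removed before any derivation when a complete record exists at the same visit. Relative to using both records, counts of subjects with suicidality can fall but not rise.

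Two stronger conclusions should be avoided. It is not true that every affected subject removes one event: the tables count subjects, one excluded record can touch several categories and the composites, and the pooled count is unchanged when the category is endorsed at another visit in the period. Nor does the rule always flatter the drug, because a positive lost at Visits 1 or 2 makes a later shift look worse.

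The size is 2 percentage points of any suicidality at about 50 per arm, or about 1 point at 93 to 97, for each subject whose only endorsement is on the excluded record. This assumes that the denominator is close to the planned arm size. The documents give neither the frequency of such record pairs nor an expected number of events, so the actual effect is unknown and may be nil.

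**What to change.** Replace the table rule in SAP section 16.6.1 with this: at each visit and for each category, use the most severe answer across all eC-SSRS records at that visit, complete or not. Add a table footnote giving the number of subjects whose positive answer appears only on an incomplete record.

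The combination should be a maximum. A rule that used the complete record only to fill blanks on the incomplete one would let a no on the incomplete form override a yes on the complete form, and so lose positives that the current rule counts.

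If the sponsor has a reason to keep the exclusion, such as technical false starts, the SAP should state it, define an incomplete record and still carry the footnote.

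The cost is a short SAP edit and a small programming change on data already collected. Counts may be slightly higher and may include some answers from abandoned forms; the footnote shows how many subjects this concerns.
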